12.3.4 Other Data

Other data collected at Screening and/or Admission will be listed by product. These data are as follows:

- Cotinine urine test
- Urine pregnancy test
- Chest x-ray
- Urine drug screen
- Serology
- Alcohol breath test
- Prior and concomitant medication
- Willingness to use CHTP 1.0
- Willingness and ability to use the products will also be summarized.

The data will be presented in the below outputs, the TFL number refers to the TFL number in the accompanying TFL shell document:

TFL number	Title
LISTINGS	
15.3.1.5	Listing of Product Test and Willingness to Use the Product
15.3.1.6	Listing of Safety Laboratory Entry Criteria
15.3.6.3	Listing of Prior and Concomitant Medication

12.4 Extent of Exposure (Product Consumption)

Details of the product test and of daily product use will be listed and summarized.

The data will be presented in the below outputs, the TFL number refers to the TFL number in the accompanying TFL shell document:

TFL number	Title
TABLES	
15.2.2.1	Descriptive Statistics of Use of CHTP Product and CC – Safety Population
15.2.2.2	Descriptive Statistics of Use of CHTP Product and CC – FAS
LISTINGS	
15.3.2.1	Listing of Product Usage

12.5 Planned Statistical Analyses

Markedly non-lognormally distributed BoExp data will be transformed or analyzed by appropriate non-parametric methods with bootstrapping using the SAS procedure PROC SURVEYSELECT. The seed to be used in any analysis will be contained in the SAS output and will be different for each analysis.

For all statistical analysis data from all arms will be included in all models.

12.5.1 Primary Analyses

12.5.1.1 COHb in blood and urinary concentrations adjusted for creatinine of MHBMA, 3-HPMA and S-PMA in 24 hour collection

COHb in blood and urinary concentrations adjusted for creatinine of MHBMA, 3-HPMA and S-PMA will be summarized as detailed in Section 12.1.3 “Descriptive Statistics”. In addition, the quantity excreted over 24 hours for each biomarkers of exposure will be presented.

The baseline is as defined in Section 12.1.4 “Definitions for Statistical Data Analysis”,

The values and percent changes from baseline in the concentration adjusted for creatinine will be listed and summarized along with the COHb concentrations and percent changes from baseline. In addition line graphs will be produced for means (and 95% CI) over all timepoints.

The transformed data will be analyzed by means of a generalized linear model using product arm as covariate adjusting for the following stratification parameters: sex and average cigarette consumption over the previous 6 weeks prior to Admission, and log-transformed baseline value of endpoint.

Assumptions of the analysis of variance model will be tested. Markedly non-lognormally distributed BoExp data will be transformed or analyzed by appropriate non-parametric methods.

The SAS code to be used is shown below:

```
Proc mixed data=_data_ ;  
Class product sex cigarette_cons ;  
Model log (Day 5) = log (baseline) sex cigarette_cons product ;  
Lsmean product / pdiff =control('CC') alpha=0.05 cl ;  
Run ;
```

The least squares (LS) means and estimate of the difference along with it's 95% CI will be back-transformed before presenting in the tables. The geometric LS means for each product along with the reduction (i.e: 100% - ratio of CHTP : CC) and 95% CI will be presented in the tables.

In addition line graphs will be produced for product geometric means (and 95% CI) over all timepoints for COHb in blood and urinary concentrations adjusted for creatinine of MHBMA, 3-HPMA and S-PMA.

The data will be presented in the below outputs, the TFL number refers to the TFL number in the accompanying TFL shell document:

TFL number	Title
TABLES	
15.2.3.1	Analysis of Biomarkers of Exposure for the Primary Objectives – FAS
15.2.3.2	Analysis of Urinary Quantity Excreted of MHBMA, 3-HPMA and S-PMA over 24 hours on Day 5 – FAS
15.2.3.3	Descriptive Statistics of Blood COHb (%) – FAS
15.2.3.3.1	Descriptive Statistics of Blood COHb (%) by Sex – FAS
15.2.3.3.2	Descriptive Statistics of Blood COHb (%) by Cigarette Consumption – FAS

TFL number	Title
15.2.3.4	Descriptive Statistics of MHBMA Urinary Concentration Adjusted for Creatinine (units) – FAS
15.2.3.4.1	Descriptive Statistics of MHBMA Urinary Concentration Adjusted for Creatinine (units) by Sex – FAS
15.2.3.4.2	Descriptive Statistics of MHBMA Urinary Concentration Adjusted for Creatinine (units) by Cigarette Consumption – FAS
15.2.3.5	Descriptive Statistics of 3-HPMA Urinary Concentration Adjusted for Creatinine (units) – FAS
15.2.3.5.1	Descriptive Statistics of 3-HPMA Urinary Concentration Adjusted for Creatinine (units) by Sex – FAS
15.2.3.5.2	Descriptive Statistics of 3-HPMA Urinary Concentration Adjusted for Creatinine (units) by Cigarette Consumption – FAS
15.2.3.6	Descriptive Statistics of S-PMA Urinary Concentration Adjusted for Creatinine (units) – FAS
15.2.3.6.1	Descriptive Statistics of S-PMA Urinary Concentration Adjusted for Creatinine (units) by Sex – FAS
15.2.3.6.2	Descriptive Statistics of S-PMA Urinary Concentration Adjusted for Creatinine (units) by Cigarette Consumption – FAS
FIGURES	
15.1.1.1	Blood COHb (%) Geometric Mean and 95% CI– FAS
15.1.1.2	MHBMA Geometric Mean Urinary Concentration Adjusted for Creatinine (units) Mean and 95% CI – FAS
15.1.1.3	3-HPMA Geometric Mean Urinary Concentration Adjusted for Creatinine (units) Mean and 95% CI– FAS
15.1.1.4	S-PMA Geometric Mean Urinary Concentration Adjusted for Creatinine (units) Mean and 95% CI– FAS
LISTINGS	
15.3.3.1	Listing of Biomarkers of Exposure and Sampling / Collection Times

The listing of the urinary biomarkers will include the concentration, the percent change in the concentration, the concentration adjusted for creatinine, the percent change in the concentration adjusted for creatinine, the volume of urine in the 24 hour collection, the quantity excreted over 24 hours and the percent change in quantity excreted over 24 hours.

The listing of the COHb data will include the concentration, the percent change in the concentration, and a flag for whether a subject's COHb is <2%.

12.5.1.2 Confirmatory Analysis

The hypothesis to be tested for each of the biomarkers of exposure of the primary objectives is that the geometric mean level on Day 5 of the biomarker for CHTP 1.0 is lower relative to CC.

Analysis of BoExp will be conducted on the natural log scale. In order to test the following hypothesis:

Null hypothesis (H_0): $m_1 \geq m_2$

Alternative hypothesis (H_1): $m_1 < m_2$

Where m_1 and m_2 are the geometric means of the biomarker levels on Day 5 for CHTP 1.0 and CC respectively.

The SAS code will be the same as described in Section 12.5.1.1 “COHb in blood and urinary concentrations adjusted for creatinine of MHBMA, 3-HPMA and S-PMA in 24 hour collection”.

12.5.2 Secondary Analyses

12.5.2.1 Biomarkers of Exposure

12.5.2.1.1 Exhaled CO

CO in exhaled breath (expressed as ppm), will be measured using the Micro+™ Smokerlyzer® or similar device, conducted on Day -2 to Day 6.

Descriptive statistics summarized by exposure will be produced separately for all timepoints for all visits applicable for exhaled CO.

Actual values and percent changes from baseline in levels of exhaled CO will be listed and summarized. In addition line graphs will be produced for product means (and 95% CI) over all timepoints.

An ANCOVA model on exhaled CO will be used with terms for the baseline value, sex, average cigarette consumption over the previous 6 weeks prior to Admission and product. The LS means for each product along with the difference (CHTP - CC) and 95% confidence interval (CI) will be presented in the tables.

12.5.2.1.2 Urinary Biomarkers of Exposure

The Urinary Biomarkers of Exposure are total 1-OHP, total NNN, 4-ABP, 1-NA, 2-NA, o-tol, CEMA, HEMA, B[a]P, HMPMA, total NNAL and NEQ. The urine parameters will be expressed as concentrations adjusted for creatinine. In addition, the quantity excreted over 24 hours for all Biomarkers of Exposure will be presented.

The values and percent changes for urinary BoExp in the quantity excreted over 24-hours and the concentration adjusted for creatinine will be listed and summarized. In addition line graphs will be produced for product means (and 95% CI) over all timepoints.

The analysis will compare the log-transformed urinary concentrations corrected for creatinine on Day 5 and the quantity excreted over 24-hours on Day 5 between the CHTP and CC arms. The descriptive statistics for each of the biomarkers of exposure of the secondary objectives, the statistical model and SAS code will be the same as described in Section 12.5.1.1 “COHb in blood and urinary concentrations adjusted for creatinine of MHBMA, 3-HPMA and S-PMA in 24 hour collection”.

The hypothesis to be tested for each of the biomarkers of exposure of the secondary objectives will be the same as described in Section 12.5.1.2 “Confirmatory Analysis”.

For the urinary concentrations, LS means for each product will be back-transformed by exponentiation and presented with the estimate and 95% CI of the reduction (calculated as the 100% - ratio).

In addition, a repeated measures ANCOVA model on the log-transformed NEQ will be used with terms for sex, average daily CC consumption over the last 6 weeks as reported during screening, product, timepoint, and the interaction between product and timepoint. The interaction term will be removed if $p > 0.1$.

The SAS code to be used is shown below:

```
Proc mixed data=_data_ ;  
Class product sex cigarette_cons time_point;  
Model log(NEQ) = sex cigarette_cons product product*time_point;  
Repeated time_point / subject=subject type=un;  
Lsmean product / diff alpha=0.05 cl;  
Run ;
```

LS means for each product will be back-transformed by exponentiation and presented with the estimate and 95% CI of the reduction (calculated as the 100% - ratio)..

TFL number	Title
TABLES	
15.2.4.1	Analysis of Biomarkers of Exposure for the Primary and Secondary Objectives – FAS
15.2.4.2	Descriptive Statistics of Exhaled CO (ppm) – FAS
15.2.4.3	Descriptive Statistics of Urinary 1-OHP – FAS
15.2.4.4	Descriptive Statistics of Urinary Total NNN – FAS
15.2.4.5	Descriptive Statistics of Urinary 4-ABP – FAS
15.2.4.6	Descriptive Statistics of Urinary 1-NA – FAS
15.2.4.7	Descriptive Statistics of Urinary 2-NA – FAS
15.2.4.8	Descriptive Statistics of Urinary o-tol – FAS
15.2.4.9	Descriptive Statistics of Urinary CEMA – FAS
15.2.4.10	Descriptive Statistics of Urinary HEMA – FAS

TFL number	Title
15.2.4.11	Descriptive Statistics of Urinary B[a]P – FAS
15.2.4.12	Descriptive Statistics of Urinary HMPMA – FAS
15.2.4.13	Descriptive Statistics of Urinary Total NNAL – FAS
15.2.4.14	Descriptive Statistics of Urinary NEQ – FAS
15.2.4.15	Analysis of NEQ over the exposure period – FAS
FIGURES	
15.1.2.1	Urinary MHBMA Quantity Excreted Over 24 hours Geometric Mean and 95% CI– FAS
15.1.2.2	Urinary 3-HPMA Quantity Excreted Over 24 hours Geometric Mean and 95% CI– FAS
15.1.2.3	Urinary SPMA Quantity Excreted Over 24 hours Geometric Mean and 95% CI– FAS
15.1.2.4	Exhaled CO Mean and 95% CI– FAS
15.1.2.5	1-OHP Urinary Concentration Adjusted for Creatinine Geometric Mean and 95% CI– FAS
15.1.2.6	Urinary 1-OHP Quantity excreted Over 24 hours Geometric Mean and 95% CI– FAS
15.1.2.7	Total NNN Urinary Concentration Adjusted for Creatinine Geometric Mean and 95% CI– FAS
15.1.2.8	Urinary Total NNN Quantity Excreted Over 24 hours Geometric Mean and 95% CI– FAS
15.1.2.9	4-ABP Urinary Concentration Adjusted for Creatinine Geometric Mean and 95% CI– FAS
15.1.2.10	Urinary 4-ABP Quantity Excreted Over 24 hours Geometric Mean and 95% CI– FAS
15.1.2.11	1-NA Urinary Concentration Adjusted for Creatinine Geometric Mean and 95% CI– FAS
15.1.2.12	Urinary 1-NA Quantity Excreted Over 24 hours Geometric Mean and 95% CI– FAS
15.1.2.13	2-NA Urinary Concentration Adjusted for Creatinine Geometric Mean and 95% CI– FAS
15.1.2.14	Urinary 2-NA Quantity Excreted Over 24 hours Geometric Mean and 95% CI– FAS
15.1.2.15	o-tol Urinary Concentration Adjusted for Creatinine Geometric Mean and 95% CI– FAS
15.1.2.16	Urinary o-tol Quantity Excreted Over 24 hours Geometric Mean and 95% CI– FAS
15.1.2.17	CEMA Urinary Concentration Adjusted for Creatinine Geometric Mean and 95% CI– FAS
15.1.2.18	Urinary CEMA Quantity Excreted Over 24 hours Geometric Mean and 95% CI– FAS

TFL number	Title
15.1.2.19	HEMA Urinary Concentration Adjusted for Creatinine Geometric Mean and 95% CI- FAS
15.1.2.20	Urinary HEMA Quantity Excreted Over 24 hours Geometric Mean and 95% CI- FAS
15.1.2.21	B[a]P Urinary Concentration Adjusted for Creatinine Geometric Mean and 95% CI- FAS
15.1.2.22	Urinary B[a]P Quantity Excreted Over 24 hours Geometric Mean and 95% CI- FAS
15.1.2.23	3-HMPMA Urinary Concentration Adjusted for Creatinine Geometric Mean and 95% CI- FAS
15.1.2.24	Urinary 3-HMPMA Quantity Excreted Over 24 hours Geometric Mean and 95% CI- FAS
15.1.2.25	Total NNAL Urinary Concentration Adjusted for Creatinine Geometric Mean and 95% CI- FAS
15.1.2.26	Urinary Total NNAL Quantity Excreted Over 24 hours Geometric Mean and 95% CI- FAS
15.1.2.27	NEQ Urinary Concentration Adjusted for Creatinine Geometric Mean and 95% CI- FAS
15.1.2.28	Urinary NEQ Quantity Excreted Over 24 hours Geometric Mean and 95% CI- FAS
LISTINGS	
15.3.3.1	Listing of Biomarkers of Exposure and Sampling / Collection Times

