The descriptive statistics of the biomarkers of the primary endpoints will also be calculated per stratification factor. Reason for change: the protocol specified that primary endpoint analyses would be done by stratification factor, and this clarifies that descriptive statistics will also be presented by stratification factor.

An analysis of plasma nicotine and cotinine and NEQ will be done covering the exposure period. Reason for change: this analysis would serve to supplement the measure of difference of exposure between CC and CHTP arms over the entire exposure period.

New parameters were added to Human Puffing Topography Assessment (Number of peak(s) in the puff, Average puff volume per peak, Average puff duration per peak) in Tables 8 and 9. Reason for change: These additional parameters would improve the assesment of topography.

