12.5.2.2 Nicotine and Cotinine Concentrations

The descriptive analysis will be the same as described in Section 12.5.1.1 “COHb in blood and urinary concentrations adjusted for creatinine of MHBMA, 3-HPMA and S-PMA in 24 hour collection”.

The change from the Day -1 sample will be calculated for the Day 5 sample. The concentrations of nicotine and cotinine will be listed and summarized along with this change. Line graphs of the nicotine and cotinine concentration profiles across all study days showing mean and 95% CI will also be produced.

For nicotine and plasma concentrations the change from baseline (Day -1 sample at 08:00 PM - 09:30 PM) on the Day 5 sample will be analyzed using an ANCOVA model with terms for baseline (Day -1) concentration, sex, average daily CC consumption over the last 6 weeks as reported during screening and product. The hypothesis to be tested for each of the biomarkers of exposure of the secondary objectives will be the same as described in Section 12.5.1.2 “Confirmatory Analysis”.

Nicotine and cotinine will also be analyzed in a repeated measures ANCOVA model, as described in section “**12.5.2.1.2 Urinary Biomarkers of Exposure**”.

The data will be presented in the below outputs, the TFL number refers to the TFL number in the accompanying TFL shell document:

TFL number	Title
TABLES	
15.2.4.16	Descriptive Statistics of Plasma Cotinine and Nicotine Concentrations (ng/mL) – FAS
15.2.4.17	Analysis of Change from Day -1 Plasma Cotinine and Nicotine Concentrations on Day 5 – FAS
15.2.4.18	Analysis of Plasma Cotinine and Nicotine Concentrations over the exposure period – FAS
FIGURES	
15.1.2.29	Plasma Cotinine and Nicotine Concentrations (ng/mL) Mean and 95% CI – FAS
LISTINGS	
15.3.3.3	Listing of Plasma Cotinine and Nicotine Concentrations and Sampling Times

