12.5.3 Exploratory Analysis

12.5.3.1 Questionnaires

12.5.3.1.1 Urge-to-Smoke Questionnaire of Smoking Urges Brief

The QSU-brief will be administered daily from Days -2 to 5.

All summaries, profiles and analysis will be presented for the CHTP and CC arms.

The change from baseline will be calculated for the total score and the two domain scores (relief and reward). The total score and two domain scores, along with the change from baseline will be summarized. The answers to the individual questions, along with the domain scores, total scores and changes from baseline will be listed.

The profiles of the raw means from baseline to Day 5 for the total score and two domain scores will be produced.

The analysis will compare each post baseline timepoint in the domain and total scores. A repeated measures ANCOVA model will be used with terms for baseline QSU-BRIEF score, sex, average daily CC consumption over the last 6 weeks as reported during screening, product, timepoint, and the interaction between product and timepoint. The interaction term will be removed if $p > 0.1$.

The SAS code to be used is shown below:

```
Proc mixed data=_data_ ;  
Class product sex cigarette_cons time_point ;  
Model reduction = base_QSU sex cigarette_cons product  
product*time_point ;  
Repeated time_point / subject=subject type=un ;  
Lsmean product / diff alpha=0.05 cl ;  
Run ;
```

LS means for each product along with the difference (CHTP - CC) with 95% CI will be presented in the tables.

All figures, summaries and analyses will be performed on the FAS.

The data will be presented in the below outputs, the TFL number refers to the TFL number in the accompanying TFL shell document:

TFL number	Title
TABLES	
15.2.4.20	Descriptive Statistics of QSU-brief Factors and Total Scores – FAS
15.2.4.21	Analysis of QSU-brief Factors and Total Scores – FAS
FIGURES	
15.1.2.31	QSU-brief Factors and Total Scores Arithmetic Mean and 95% CI – FAS
15.1.2.32	QSU-brief Factors and Total Scores Arithmetic Least Squares Mean Differences and 95% CI – FAS
LISTINGS	
15.3.6.11	Listing of QSU-brief Questionnaire Results and Changes from Baseline

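### The over-time models for NEQ, nicotine and cotinine leave out baseline, and the NEQ and QSU-brief code omits the time main effect, so the p > 0.1 rule as coded uses an 8-df test instead of the 4-df interaction test

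*SAP*

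**What the plan says.** SAP 12.5.2.1.2 adds a repeated-measures ANCOVA of log NEQ. The text names sex and cigarette consumption, then "product, timepoint, and the interaction between product and timepoint". It gives no baseline term. It continues: "The interaction term will be removed if" its p-value exceeds 0.1. The code given for use is "Model log(NEQ) = sex cigarette_cons product product*time_point", which has neither a baseline nor a `time_point` main effect.

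SAP 12.5.2.2 extends the model: "Nicotine and cotinine will also be analyzed in a repeated measures ANCOVA model", with a cross-reference to 12.5.2.1.2. For the Day 5 comparison of nicotine and cotinine, the same section does include "terms for baseline (Day -1) concentration". The Day 5 NEQ analysis adjusts for log baseline through the model of 12.5.1.1.

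Section 9 explains why the over-time analysis was added: "this analysis would serve to supplement the measure of difference of exposure between CC and CHTP arms over the entire exposure period".

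For QSU-brief (12.5.3.1.1) the text has "terms for baseline QSU-BRIEF score", a timepoint term, the interaction and the same removal rule. The code begins "Model reduction = base_QSU sex cigarette_cons product" and then adds only the interaction, so baseline is present but the time main effect is again missing. MCEQ and MNWS (12.5.3.1.2 and 12.5.3.1.3) list a baseline score and reuse the QSU-brief code, but state no removal rule.

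**The concern.** Baseline is missing only from the nicotine-exposure models. NEQ and plasma nicotine and cotinine are all measured on Day -2 and Day -1 (protocol Appendix A, Tables A1 and A2), and SAP 12.1.4 defines baseline as the last valid value before Day 1. The covariate therefore exists, is used elsewhere for the same analytes, and is left out here without a stated reason. The price is a wider interval for the comparison of nicotine exposure over the whole period.

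The second problem is that text and code give different tests for a pre-specified decision. Without a time main effect, the product-by-time term has to carry the common day-to-day trend as well as the difference between arms. A small p-value may then only mean that both arms drifted together. If the term is dropped, the two versions also leave different models: the text keeps time, while the code keeps no time term.

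This matters most for QSU-brief. Section 9 includes the interaction there so that the pattern over time can be seen; once it is dropped, the CHTP minus CC difference is constant over days by construction.

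**Working it through.** The SAP states no degrees of freedom or precision for these models, so there is no figure of its own to reproduce.

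**Inputs from the documents.** Two arms, 40 subjects each (SAP Section 8). Five time points: the NEQ, nicotine and cotinine models cover the exposure period (Section 9), defined as Day 1 to Day 5, and the QSU-brief model uses post-baseline points only.

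**Inputs assumed.** Log-scale SD and correlations between days. The documents give neither.

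**1. Degrees of freedom** (ranks of the product and time part; sex and consumption add the same amount to each)

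| | With interaction | Without it | Df tested |
|---|---|---|---|
| As coded: product, product × time | 10 | 2 | 10 − 2 = 8 |
| As in the text: product, time, product × time | 10 | 6 | 10 − 6 = 4 |

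Both full models have rank 10 and the same fit, so product LS means and contrasts are identical while the term is kept.

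**2. What the 8-df test responds to.** Take SD 0.5 and correlation 0.6. The within-subject variance is 0.25 × (1 − 0.6) = 0.10. A linear change of 0.10 over five days has a sum of squares about its mean of 2 × (0.05² + 0.025²) = 0.00625.

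- Common fall of 0.10 in both arms: the 8-df noncentrality is 2 × 40 × 0.00625 / 0.10 = 5.0; the 4-df noncentrality is 0.
- Opposite drifts of 0.10 per arm: the 8-df value is again 5.0. The arm difference changes by 0.20 (sum of squares 0.025), so the 4-df value is 20 × 0.025 / 0.10 = 5.0.
- Drift of 0.20 in one arm only: the 8-df value is 40 × 0.025 / 0.10 = 10.0; the 4-df value is 5.0.

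**3. How often the term is kept (p ≤ 0.1).** Simulation with 20,000 runs per case, compound-symmetric data, estimated unstructured covariance and F tests on 76 denominator df:

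| Scenario (SD 0.5, correlation 0.6) | Coded 8-df test | 4-df test |
|---|---|---|
| No trend, no interaction | 11.6% | 11.7% |
| Common fall 0.05 | 18.8% | 11.3% |
| Common fall 0.10 | 42.8% | 10.9% |
| Common fall 0.20 | 94.9% | 11.3% |
| Opposite drifts, 0.10 per arm | 42.6% | 52.8% |
| Drift of 0.20 in one arm | 70.3% | 52.9% |

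Over SD 0.3 to 0.7 and correlation 0.3 to 0.8, the coded test keeps the term in 14–55%, 20–99% and 48–100% of trials for common falls of 0.05, 0.10 and 0.20.

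**4. Effect on the mean contrast after removal** (2,000 runs per case, coded rule). Full against reduced model: −0.1000 and −0.1017 (opposite drifts); −0.1038 and −0.1051 (one arm); 0.0064 and 0.0063 (common fall 0.10). The largest shift is 0.0017 log units, and the SE ratio is 0.97 in each case. With complete data the reduced contrast is the same with or without `time_point`.

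**5. Precision given up without baseline.** The interval for the five-day mean narrows by 1 − √(1 − c²), where c is the correlation of baseline with that mean, read as what remains after sex and consumption stratum.

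- Correlation decaying as r to the power of the lag: 4.3% (r = 0.5), 13.1% (0.7), 22.5% (0.8), 39.8% (0.9).
- Baseline correlation rb with exposure days that correlate rw with each other, c = rb / √((1 + 4rw)/5). For rb = 0.2 and rw = 0.8, c = 0.2 / √0.84 = 0.218, giving 2.4%. Other pairs: 6.9% (0.3, 0.6), 16.2% (0.5, 0.8), 31.4% (0.6, 0.6). This case allows for one arm changing product between baseline and Day 1.
- Constant correlation: 10.8% (0.3), 23.6% (0.5), 51.2% (0.8).

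**The case against.** The strongest reply is that the 8-df test arises only if the programmer follows the code over the text. The text names the timepoint term and speaks of removing the interaction; following it gives the 4-df test and keeps time. Parts of the SAP's code also read like a template. That is fair, but the SAP presents the block as the code to be used, so the two instructions conflict and one must be corrected.

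A second reply is that little depends on the decision. For NEQ, nicotine and cotinine this stands: the contrast is identical if the term is kept and almost unchanged if it is dropped. For QSU-brief, the constant difference after removal follows from having a removal rule at all; the coding gap only changes how often removal happens. Descriptive profiles are planned regardless, Section 9 makes the comparison over all time points the main one, and QSU-brief is exploratory.

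Third, nothing in the documents predicts a common drift, and where only one arm drifts the coded test keeps a real interaction more often. This also stands: the direction of the error depends on the pattern.

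Fourth, randomisation protects against bias without baseline, the analysis is a declared supplement, and the Day 5 models already adjust. The gain also depends on the correlation left after sex and consumption stratum, which is unknown. All true, but none of it is a reason to omit a covariate already collected.

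**Conclusion.** The concern holds as a minor point. Three facts need no assumption: the NEQ, nicotine and cotinine over-time models have no baseline; the NEQ and QSU-brief code lacks the time main effect listed in the text; and the coded interaction test has 8 df where the described one has 4. The sizes do rest on assumptions: a precision gain of 2% to 51% across the correlation patterns tried, and a removal rule that can err in either direction. The fault lies in the rule and in lost precision, not in bias of the overall contrast. The primary endpoints, their power and the Day 5 comparisons are not affected.

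**What to change.** Add the baseline value, on the log scale where the outcome is logged, to the text and code of the NEQ, nicotine and cotinine over-time models. Write the fixed effects in all repeated-measures code as baseline, sex, `cigarette_cons`, `product`, `time_point` and `product*time_point`, so that the p > 0.1 rule uses the 4-df test and time stays if the interaction goes. Alternatively, delete the rule and keep the interaction throughout.

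The cost is a few lines of SAP text and code, and 1 df per model for baseline. A subject with no valid pre-Day 1 value would drop out of these models; with samples on both Day -2 and Day -1 and baseline defined as the last valid value, that should be rare.

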12.1.3 Descriptive Statistics

For continuous data, summary statistics will include the number of subjects (n), the number and percent of subjects with missing data, the arithmetic mean, arithmetic SD, median, first and third quartiles, minimum, maximum, and number; for log-normal data the geometric mean and geometric CV will also be presented. For categorical data, frequency counts and percentages will be presented. Data listings will include all subject level data collected unless otherwise specified. Summary statistics and statistical analyses will generally only be performed for subjects included in the relevant analysis population. For the calculation of summary statistics and statistical analysis, unrounded data will be used.

Summaries on the Safety Population will be produced by actual exposure. Subjects who tested the product but were discontinued before randomization will be shown in a separate column /table.

The following product labels will be used throughout the TFLs (**Table 17**):

Table 17: Product Labels		
Product	Format used in TFLs	Order in TFLs
Carbon Heated Tobacco Product	CHTP	1
Conventional cigarettes	CC	2

The following stratification labels (**Table 18**) for the TFLs will be used:

Table 18: Stratification Labels	
Stratification Factor	Definition
Sex	male
	female
Daily CC consumption (per day)	<10 ¹
	10-19
	>19

¹ Note that due to inclusion criteria for the study there should not be any subjects with daily CC consumption < 10, therefore this category will not be presented unless there is sufficient data for analysis/presentation (see Section 12.1.5.1 "Insufficient Data for Analysis/Presentation").

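### The exposure-period nicotine models name no reference arm, so the code as written would probably return CC:CHTP instead of the CHTP:CC ratio that the reduction needs

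*SAP*

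**What the plan says.** Three parts of the SAP bear on the direction of the product contrast.

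- **Primary analysis (12.5.1.1).** The code names the reference: "Lsmean product / pdiff =control('CC') alpha=0.05 cl". The text defines the effect to be tabulated: "The geometric LS means for each product along with the reduction (i.e: 100% - ratio of CHTP : CC) and 95% CI". Section 12.5.2.1.2 uses this code for the Day 5 urinary biomarkers, NEQ included.
- **NEQ over the exposure period (12.5.2.1.2).** The repeated-measures code has the CLASS statement "Class product sex cigarette_cons time_point", with no ordering or reference option, and the contrast "Lsmean product / diff alpha=0.05 cl". The back-transformed LS means are to be "presented with the estimate and 95% CI of the reduction (calculated as the 100% - ratio"). The arms forming that ratio are not restated here. Section 12.5.2.2 refers plasma nicotine and cotinine to this model.
- **Questionnaires (12.5.3.1.1 to 12.5.3.1.3).** The QSU-brief code has the same plain `diff`, and MCEQ and MNWS reuse it. The text gives the direction: "LS means for each product along with the difference (CHTP - CC) with 95% CI will be presented in the tables". The response in the code is a variable called `reduction`, which the SAP does not define; the text speaks of comparing scores.

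Table 17 in 12.1.3 ("The following product labels will be used throughout the TFLs") lists CHTP as order 1 and CC as order 2.

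**The concern.** The SAP fixes the contrast in one code block and leaves it to the software in the two repeated-measures blocks. For a difference, a reversed contrast changes only the sign. For a reduction computed as 100% minus a ratio it changes the size as well, because inverting the ratio does not simply change the sign of the reduction.

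The point matters most for nicotine. SAP Table 11 expects primary biomarker ratios of 0.15 to 0.40, where a reversal would be obvious: at 0.40 a 60% reduction would appear as 100 × (1 - 1/0.40) = -150%. For nicotine, Protocol 2.1.1 describes the aim as delivery close to that of cigarettes. The ratio may therefore lie near 1, where either sign looks plausible. The exposure-period table (15.2.4.15) could then disagree with the Day 5 NEQ result in Table 15.2.4.1 for no reason but the code.

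**Working it through.** The documents give no figure for this contrast, so there is none to reproduce. The check has three steps. The ratios are assumed for illustration.

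**1. Which arm comes first?** This rests on an assumption about the software that the documents do not state: PROC MIXED sorts CLASS levels by formatted value, and plain `diff` gives first minus second.

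| Coding of product | Sorted order | Plain `diff` returns |
|---|---|---|
| 'CHTP', 'CC' | CC, CHTP | CC - CHTP |
| 'CHTP 1.0', 'CC' | CC, CHTP 1.0 | CC - CHTP 1.0 |
| unformatted 1 = CHTP, 2 = CC | 1, 2 | CHTP - CC |

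The primary code refers to a level that reads 'CC', and Table 17 gives CHTP and CC as formats. Both favour the first row. The third row is possible but fits the SAP's own code poorly.

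**2. Effect on the reported reduction.** Let r be the true CHTP:CC ratio.

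- Intended: 100 × (1 - r)
- From CC - CHTP, back-transformed as it stands: 100 × (1 - 1/r)

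| r | Intended reduction | With the ratio inverted |
|---|---|---|
| 0.50 | 50% | 100 × (1 - 2.00) = -100% |
| 0.80 | 20% | 100 × (1 - 1.25) = -25% |
| 0.90 | 10% | 100 × (1 - 1.111) = -11.1% |
| 1.10 | -10% | 100 × (1 - 0.909) = +9.1% |
| 1.20 | -20% | 100 × (1 - 0.833) = +16.7% |

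The interval moves too. With r = 0.80 and an assumed 95% CI of 0.70 to 0.90, the intended reduction is 20% (10% to 30%). The inverted one is -25% (-42.9% to -11.1%), from 100 × (1 - 1/0.70) and 100 × (1 - 1/0.90). On the log scale only the sign of the estimate changes, so two-sided p-values and interval widths on that scale stay the same.

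**3. Questionnaires.** The result depends on what `reduction` means. With baseline score as a covariate, the product effect on (baseline - score) is exactly minus the product effect on the score. A simulated data set with 40 subjects per arm, in which the adjusted CHTP - CC difference in score was +0.337, gives:

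| Response modelled | Plain `diff` (CC - CHTP) | `diff=control('CC')` (CHTP - CC) |
|---|---|---|
| score | -0.337 | +0.337 |
| change (score - baseline) | -0.337 | +0.337 |
| baseline - score | +0.337 | -0.337 |

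If `reduction` is baseline minus score, the two sign changes cancel: plain `diff` already equals CHTP - CC in scores, and naming CC as control would itself reverse it.

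**The case against.** The best defence is that the intended direction is not in doubt. 12.5.1.1 and 12.5.3.2 both define the reduction from CHTP:CC, no other ratio appears in the SAP, and the questionnaire sections state CHTP minus CC. The snippets are partly schematic: the primary code models 'log (Day 5)', and the NEQ text lists timepoint as a term while its code has only the interaction. A programmer must adapt them and could put the contrast right. LS means by arm are to be shown next to the effect, so geometric means of 8 (CHTP) and 10 (CC) beside a reduction of -25% would contradict each other. Section 12.5.2.2 refers to the model, not expressly to the code, so the carry-over to plasma nicotine and cotinine is inferred. The level order is inferred too.

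Most of this stands, and it limits the point to a risk. It does not remove it: 12.5.2.1.2 presents this as the code to be used, it differs from the SAP's own primary code, and the text beside it does not say which arm is the numerator.

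A reader might infer more: that the tabulated nicotine reductions and the questionnaire differences will come out reversed. The documents do not support that. They state neither the coding of product nor the ordering rule, and for the questionnaires the undefined response leaves the sign open.

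**Conclusion.** The point holds for NEQ over the exposure period and, if the same code is used, for plasma nicotine and cotinine. Run as written, with levels named CC and CHTP and default sorting, the code returns CC - CHTP. Used without checking direction, it would give a reduction of the wrong sign and size: -25% for a true 20% reduction, or a 16.7% reduction when exposure is 20% higher on CHTP. This rests on the level names implied by the SAP, the default SAS ordering, and back-transformation of the contrast as printed.

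For QSU-brief, MCEQ and MNWS the conclusion is narrower: the code does not determine the direction, because its response is undefined.

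The primary analysis and the Day 5 analyses are unaffected, and so are the p-values. The exposure-period nicotine models are supplementary additions made in SAP section 9, and the questionnaires are exploratory.

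**What to change.** 1. In the NEQ code of 12.5.2.1.2, replace plain `diff` by `diff=control('CC')`.
2. State in 12.5.2.1.2 and in 12.5.2.2 that the ratio is CHTP:CC and the reduction is 100% minus that ratio. Say in 12.5.2.2 that the same code applies.
3. In 12.5.3.1.1, first replace the response `reduction` by the questionnaire score, or define it. With the score as response, use `diff=control('CC')`, so that the output is the stated CHTP - CC difference. MCEQ and MNWS inherit both changes. The order matters: if `reduction` means baseline minus score, naming the control alone would reverse the reported difference.

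The cost is one option in each of two code blocks, one response variable and a sentence or two of text. With two arms, naming the control changes only the direction of the contrast, not its standard error or p-value.
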